8.1 Primary Objective

The primary endpoint will be the evaluation at week 12/16 of the sensitivity and the specificity, compared to the DLQI as a standard, of the PSO-TARGET QoL component grid to assess the level of satisfaction of patient achieving the therapeutic goal, identified by himself.

The therapeutic objective will be considered as achieved if the patient gives the responses "Satisfied" or "Very Satisfied" on the Likert scale. The response will then be compared to the DLQI score at 12/16 weeks.

8.2 Secondary Objectives

- Evaluate the percentage of patients who consider their target objective as being achieved after 12/16 weeks of treatment as defined by a "satisfied or very satisfied" response.
- Level of concordance between the satisfaction level in regard to the therapeutic objective set by the PSO-TARGET QoL Component grid and the DLQI at the 2nd follow-up visit (52 ± 4 weeks.).
- Evaluate the level of agreement between the dimensions reported by the patient and by the treating physician at baseline.
- Follow the degree of completeness of the main treatment goal identified at baseline after 52 weeks.
- Follow evolution of the PASI score (at 12/16 and 52 weeks).
- Level of accordance between PASI 90/100 and the satisfaction level in regard to the therapeutic objective set by the PSO-TARGET QoL Component grid.
- Follow evolution of the DLQI score (at 12/16 and 52 weeks).
- Evaluate the rate of patients who change their therapeutic objective after 12/16 weeks of treatment.

9 Research Method

9.1 Study Design

9.1.1 Eligibility criteria

The inclusion criteria are the following:

- Age > 18 years

THIS DOCUMENT CONTAINS TRADE SECRETS, AND/OR COMMERCIAL OR FINANCIAL INFORMATION, PRIVILEGED OR CONFIDENTIAL, DELIVERED IN CONFIDENCE AND RELIANCE THAT SUCH INFORMATION WILL NOT BE COPIED OR MADE AVAILABLE TO ANY THIRD PARTY WITHOUT THE WRITTEN CONSENT OF LEO PHARMA A/S

- Patient for whom the dermatologist decided to initiate a treatment by Kyntheum® according to SmPC.
- Patient who signed an informed consent.

The following non-inclusion criteria will be applied:

- Vulnerable subjects according to the law;
 - pregnant, parturient or breast feeding women;
 - deprived of their freedom by administrative, medical or legal decision or who is under trusteeship/guardianship;
 - legally protected, or unable to express their consent to participate;
 - With no affiliation to a social security system;
- Psychologically/linguistically unable to express their consent to participate;
- With an hypersensitivity to at least one of the excipients of Kyntheum®;
- Participating at the same time in another clinical trial.

9.1.2 PSO-TARGET Quality of Life Component grid.

As a first step to construct the component grid, a retrospective survey based on the recollection and experience from 3 clinical dermatologists (2 French and 1 Belgian) of patient's expectations, has been conducted. The results of the survey have been used to generate a grid containing 12 therapeutic goals equally distributed into the 4 major psychometric components classically used in quality of life studies in patients suffering from chronic diseases (Chassany, 2003; Forestier et al., 2019). These four dimensions (cf table 1) are the following:

- **Physical:** autonomy, physical capabilities, ability to perform daily activities;
- **Subjective:** linked to experienced emotion, anxiety, well-being;
- **Relational/social:** with family, friendship or professional environment, engaging personal relationships, involvement in social or leisure activities;
- **Therapeutic:** linked to treatment, for ex. treatment-/care-related discomfort.

The investigators participating to the study will agree to implement this table as part of their standard of care along with the DLQI questionnaire.

Table 1: Quality of Life (QoL) component grid

Physical	Subjective	Relational/ social	Therapeutic
----------	------------	--------------------	-------------

THIS DOCUMENT CONTAINS TRADE SECRETS, AND/OR COMMERCIAL OR FINANCIAL INFORMATION, PRIVILEGED OR CONFIDENTIAL, DELIVERED IN CONFIDENCE AND RELIANCE THAT SUCH INFORMATION WILL NOT BE COPIED OR MADE AVAILABLE TO ANY THIRD PARTY WITHOUT THE WRITTEN CONSENT OF LEO PHARMA A/S

Not be limited/handicapped by the pain	Think less or not at all about the disease	Spend quality time with family, friends or colleagues	Need to think less about treatment and care
Do not feel any functional discomfort (itching, rash) in my daily activities	Do not feel any anxiety from the disease	Not caring about what people think about me	Encounter very few, if any, drug discomfort
Have freedom of movement and activities	Feel serene, have peace of mind	Have a fulfilling intimate life	To be cured quickly

This grid will be administered to the enrolled patients after signature of the informed consent. The patient will be requested to identify what would be his/her main treatment objective. Only one item from the list will be picked by the patient. The investigator must not influence the patient into choosing a specific component to the table. The patient will have a grid with 12 proposals in front of him/her and will not be aware of the dimensions to which the proposals relate. The four dimensions typically described in chronic diseases will be considered only for analysis, but not submitted to patients. The patient will be given some space and time to choose the component without any help or supervision from the investigator. This is requested in order to avoid social desirability, defined as the tendency of some respondents to report an answer in a way they deem to be more socially acceptable than would be their "true" answer. The patient will then conceal his/her response in a provided envelope without revealing the chosen component to the physician.

In the meantime, the treating physician will identify the therapeutic objective that is supposedly the most important for his patient, based on his/her discussion with him. The physician-reported component will be concealed in a separate envelope and compared with the patient-chosen component during the analysis of the secondary endpoints.

As the primary endpoint of the study, the level of achievement of this therapeutic goal at 3 months (12/16 weeks) will be assessed by a 4-points Likert scale (Very Unsatisfied; Unsatisfied; Satisfied; Very Satisfied), and compared to the DLQI scoring classes.

9.1.3 Dermatology Quality of Life Index (DLQI)

The DLQI is designed to measure the health-related quality of life of adult patients suffering from a skin disease. It can be administered in patients aged 16 years and over and takes only few minutes to complete. The DLQI consists of 10 questions concerning patients' perception of the impact of skin diseases on different aspects of their health-related quality of life over the last week. It is not specific to psoriasis and is the most frequently used patient reported

outcome measure in randomised controlled trials in dermatology in general and in psoriasis more specifically (Cardiff University, 2019; Puig et al., 2017).

The DLQI is composed of ten questions grouped in 6 domains “symptoms and feelings”, “daily activities”, “leisure”, “work/school”, “personal relationships” and “treatment”. To each question the patient will have the followings choices: “Very much”, “A lot”, “A little”, “Not at all” or “not relevant”

Each answer is graded from 0 (“not relevant”, “not at all” or not answered) to 3 (“very much”). The DLQI is calculated by adding the score of each question, resulting in a maximum of 30 and a minimum of 0. The higher the score, the more quality of life is impaired. A score higher than 10 indicates that the patient's life is being severely affected by their skin disease (Finlay and Khan, 1994).

More specifically, the total score will be divided into the following subcategories:

- 0-1 = no effect at all on patient's life;
- 2-5 = small effect on patient's life;
- 6-10 = moderate effect on patient's life;
- 11-20 = very large effect on patient's life;
- 21-30 = extremely large effect on patient's life.

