9.5 Study Size

The main criterion is the sensitivity of the PSO-TARGET tool (percentage of patients who consider their target objective as being achieved after 12/16 weeks of treatment as defined by a "satisfied or very satisfied" response, assessed on a 4 points Likert scale, among patients with a DLQI total score of 0 or 1).

The sample size calculation is based on the following hypotheses:

Sensitivity: 90%

Absolute precision : 10%

Type I error : 5%

Power at 80%

Prevalence: 80% (estimated rate of patient with a DLQI 0-1 after 12 weeks of treatment)

Hypothesis :

THIS DOCUMENT CONTAINS TRADE SECRETS, AND/OR COMMERCIAL OR FINANCIAL INFORMATION, PRIVILEGED OR CONFIDENTIAL, DELIVERED IN CONFIDENCE AND RELIANCE THAT SUCH INFORMATION WILL NOT BE COPIED OR MADE AVAILABLE TO ANY THIRD PARTY WITHOUT THE WRITTEN CONSENT OF LEO PHARMA A/S

$H_0 : Se = Se_0$

$H_1 : Se = Se_1 > Se_0$

With Se =sensitivity, $Se_0=0.8$ and $Se_1=0.9$

Using the binomial probability formula, the sample size necessary to meet both a significance level and a power requirement may be found by solving the following two equations simultaneously :

Significance level $B(s_1 > s \alpha | n_1, Se_0) = \alpha$

$B(s_1 > s \alpha | n_1, Se_1) = 1 - \beta$

Where n_1 : patients with a DLQI 0-1, s_1 : patients with a DLQI 0-1 and a positive test outcome

With $\alpha=0.05$ and $1 - \beta=0.8$

To obtain n , n_1 is inflated by the prevalence P (rate of patients with a DLQI 0-1 = 80%), to obtain $n = n_1 / P$

The software used is PASS version 12, using the Li and Fine method (Li and Fine, 2004).

Based on these hypotheses, the sample size needed is estimated at 134 evaluable patients.

Assuming 10% of patients will not be evaluable on main criterion, **150 patients have to be included.**

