9.8 Statistical Analysis Plan

Data analyses will be performed using SAS Version 9.4 or further (SAS Institute, Cary, NC USA software).

Quantitative parameters will be described using the following summary descriptive statistics: number of non-missing values, mean, standard deviation, median, first and third quartiles, and minimum and maximum values.

Qualitative parameters will be described overall using frequencies and percentages. Percentages will be calculated on the number of non-missing observations.

The level of significance for all comparisons is set at 0.05 using two-tailed tests. Confidence intervals at 95% could be provided, if relevant.

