9.8.3 Sensitivity/sensibility analysis

- Analysis of the primary endpoint

The primary endpoint will be the evaluation at week 12/16 of the sensitivity and the specificity, compared to the DLQI as a standard, of the PSO-TARGET QoL component grid to assess the level of satisfaction of patient achieving the therapeutic goal, identified by himself.

The therapeutic objective will be considered as achieved if the patient gives the responses “Satisfied” or “Very Satisfied” on the Likert scale. The response will then be compared to the DLQI score at 12/16 weeks.

It will be described on the efficacy population.

A contingency table will be constructed as follows:

PSO-TARGET \ DLQI	0-1	2-5	6-10	11-20	21-30
Very satisfied	TP	FP	FP	FP	FP
Satisfied	TP	FP	FP	FP	FP
Unsatisfied	FN	TN	TN	TN	TN
Very unsatisfied	FN	TN	TN	TN	TN

This table can be summarized as :

PSO-TARGET \ DLQI	0-1	≥ 2
Very satisfied ou Satisfied	TP	FP
Unsatisfied ou Very unsatisfied	FN	TN

TP: True positive

FP: False Positive

FN: False Negative

TN: True Negative

The validity of the QoL component grid will then be assessed by calculating the following parameters:

Sensitivity: defined as the probability to have patients who have reached their therapeutic target (who have responded « satisfied » or « very satisfied » on the Likert scale, globally and in each major domains) among patients with a DLQI score between 0 and 1.

In other terms the sensitivity is defined as the **concordance** of the QoL component grid and the DLQI **for the patients with optimal quality of life**.

The sensitivity is calculated by:

$$Se = \frac{TP}{TP + FN}$$

Specificity: defined as the probability to have patients who have not reached their therapeutic target (who have responded « unsatisfied » or « very unsatisfied » on the Likert scale, globally and in each major domains) among patients with a DLQI score ≥2.

In other terms the specificity is defined as the **concordance** of the QoL component grid and the DLQI **for the patients with suboptimal quality of life**.

The specificity is calculated by:

$$Sp = \frac{TN}{FP + TN}$$

The QoL component grid will be validated if these two parameters reach the threshold of 85%.

THIS DOCUMENT CONTAINS TRADE SECRETS, AND/OR COMMERCIAL OR FINANCIAL INFORMATION, PRIVILEGED OR CONFIDENTIAL, DELIVERED IN CONFIDENCE AND RELIANCE THAT SUCH INFORMATION WILL NOT BE COPIED OR MADE AVAILABLE TO ANY THIRD PARTY WITHOUT THE WRITTEN CONSENT OF LEO PHARMA A/S

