Objective	Statistical analysis	Exposure measure	Outcome measure	Covariates
1	Contingency table; Sensitivity / Specificity	N/A	Concordance level between PSO- TARGET Component grid and DLQI at 12/16 weeks	N/A

- Analysis of the secondary performance endpoints

Analyses of secondary endpoints will be performed on the efficacy population.

No replacement of missing data will be performed.

The same analysis as the primary performance analysis will be performed at 52 weeks.

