9.8.4 Efficacy analysis

- Secondary objective/endpoint : achievement of target objective at 12 weeks, per component

Evaluation at week 12/16 of the level of achievement of the main treatment goal identified by the patient in the table at baseline. This evaluation will be performed using a Likert scale in 4 points (“very satisfied”, “satisfied”, “unsatisfied”, “very unsatisfied”).

The achievement of the main treatment goal will be defined as a “satisfied or very satisfied” response.

It will be described on the efficacy population.

- The proportion of patients with achievement of the main treatment goal will be described and the confidence interval at 95% will be provided.
- The primary analysis will be performed with considering missing data as non responder, and a sensitivity analysis will be performed on patients without missing data (observed case).
- Search for predictive factors of efficacy.

The predictive factors of the achievement of the main treatment goal on completed patients will be searched among baseline characteristics using binary logistic regressions models. Univariate analyses will be used to select ($p\text{-value} \leq 0.20$) the explanatory variables to include

in the multivariate model. The results of univariate and multivariate analyses will be interpreted in terms of odds-ratios with their 95% confidence intervals

In case of correlated variables, only the more significant in univariate will be include in the multivariate model.

Variables with a rate of missing data $\geq 20\%$, or those with empty categories or with very small number will not be considered eligible for this research of predictive factors.

As part of one of the secondary objectives, the analyses performed for the efficacy endpoint are summarized in the table below :

Objective	Statistical analysis	Exposure measure	Outcome measure	Covariables
2.a	Proportions	N/A	Achievement of the main goal (yes /no) at 12/16 weeks	N/A
2.b	Proportions – sensitivity analysis	N/A	Achievement of the main goal (yes /no) at 12/16 weeks	N/A
2.c	Binary logistic regression models,	N/A	Achievement of the main goal (yes /no) at 12/16 weeks	Relevant confounders (eg : demographic data, medical history, previous treatment...)
2.d	Proportions	N/A	Achievement of the main goal (yes /no) at 12/16 weeks for each component	N/A

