9.9.1 Data Collection

Data will be collected on printed CRFs by the investigators. The completed CRFs as well as the completed questionnaires will be sent to the CRO and entered by a data manager into a computer database developed specifically for this study.

Data will remain anonymous.

Access to the database will be restricted to personnel responsible for data entry and to data management and statistics personnel who are directly involved in the management or analysis of this study. Investigators will not have access to the computer database.

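### DLQI scoring gives an unanswered item 0 with no limit on how many are unanswered, so an incomplete form can be counted as DLQI 0-1 in the primary table when its true total could be 2 or more

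*Protocol*

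**What the plan says.** Protocol section 9.1.3 fixes the item scores: "Each answer is graded from 0 (“not relevant”, “not at all” or not answered) to 3 (“very much"). It then fixes the total: "The DLQI is calculated by adding the score of each question, resulting in a maximum of 30 and a minimum of 0". It names no minimum number of answered items and no condition under which a form cannot be scored.

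Section 9.8.3 cuts that total at 0-1 against 2 or more and uses the cut as the reference standard. Sensitivity is taken among the 0-1 patients and specificity among the rest. The decision rule is "The QoL component grid will be validated if these two parameters reach the threshold of 85"%.

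Other provisions come close but do not set a limit:

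- Section 9.5 enlarges the sample: "Assuming 10% of patients will not be evaluable on main criterion". It does not define evaluable by items answered.
- Section 9.8 says "Percentages will be calculated on the number of non-missing observations".
- Section 9.4 makes the DLQI mandatory, section 9.6 asks for complete data sets where possible, and section 9.9.3 provides for queries and a check on missing data.
- Section 9.9.1 says "the completed questionnaires will be sent to the CRO and entered by a data manager into a computer database".

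**The concern.** A skipped question carries no information, yet the rule reads it as evidence of no impairment. Because a skip can only lower a total, patients can move from 2 or more into 0-1 and never the other way. The 0-1 class is the most exposed, since one lost item can be enough to reach it. A form whose answered items already sum to 2 or more is safe, because its class is certain.

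The rule in section 9.8 on non-missing observations does not help: under section 9.1.3 an unanswered item has a score, so the total is never missing.

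A misplaced form acts on both measures. It joins the sensitivity denominator, where an unsatisfied patient counts as a false negative. It also leaves the specificity denominator, which is small on the plan's own figures. At stake is a pass/fail verdict at 85% on each.

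**Working it through.** **Inputs from section 9.5:** Se0 = 0.80, Se1 = 0.90, type I error 5%, power 80%, prevalence of DLQI 0-1 = 80%, 134 evaluable, 150 included. **From section 9.8.3:** the cut at 0-1 against 2 or more, and the 85% threshold. **Assumed, because the protocol gives no figure:** 2-6% of forms incomplete, regardless of DLQI class.

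**1. The plan's sample size.** An exact binomial test with upper tail 0.025 first reaches 80% power at n1 = 107 (critical value 94, tail 0.0233, power 0.819). Then 107/0.80 = 133.75, so 134, as stated. The expected table has 107 patients at DLQI 0-1 and 134 - 107 = 27 at 2 or more.

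**2. What skips can hide.** With recorded sum s (0 or 1) and k skipped items, the true total can be as high as s + 3k: 4 for one skip, 7 for two. One skip can bring a total of 2, 3 or 4 down to 0-1, but never 5 or more.

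**3. Upper bound on forms moved.** Let every incomplete form from a DLQI 2-or-more patient fall to 0-1:

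- 27 x 0.02 = 0.54 and 27 x 0.06 = 1.62 forms.
- Planned true positives: 0.90 x 107 = 96.3.
- All moved patients unsatisfied: 96.3/107.54 = 89.5% and 96.3/108.62 = 88.7%.
- All moved patients satisfied: 96.84/107.54 = 90.1% and 97.92/108.62 = 90.1%.
- Shift from 90%: -1.3 to +0.1 points.

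**4. Specificity near the threshold.** Of 27:

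- 23/27 = 85.2% passes. One unsatisfied patient moved gives 22/26 = 84.6%, and two give 21/25 = 84.0%; both fail.
- 22/27 = 81.5% fails. Two satisfied patients moved give 22/25 = 88.0%, a pass; one gives 22/26, still a fail.
- If one or two patients of the same kind move, no other count from 19 to 27 changes verdict.

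**5. Probability that a verdict changes.** Take TN ~ Bin(27, Sp), with each patient moving independently with probability r, whatever the satisfaction, and sum exactly. At true Sp 85% under the upper bound (r = 0.02 and 0.06), the specificity verdict changes with probability 7.3% and 13.1%, of which 7.25 and 12.5 points are pass to fail. For sensitivity, with TP ~ Bin(107, Se) and moved patients satisfied with probability 15%, the figures are 4.9-14.4% at true Se 85% and 1.5-5.7% at 90%.

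**6. A less extreme case.** Assume one skip per incomplete form, equally likely on any of ten items. The most exposed pattern is a total of 2 made of 1 + 1, where 2 of 10 possible skips lead to 0-1. Even if all 27 patients had that pattern, r is 0.2 x 0.02 = 0.004 to 0.2 x 0.06 = 0.012. That moves 27 x 0.004 = 0.11 to 27 x 0.012 = 0.32 forms. The specificity verdict at true Sp 85% then changes with probability at most 1.8-4.9%.

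**7. What exclusion can do.** Suppose 23/27 has become 22/26 because one unsatisfied patient was recorded as 0-1. Leaving that form out of the table still gives 22/26. Only counting it as 2 or more restores 23/27.

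**The case against.** The strongest reply is that the effect is slight and the safeguards are real. The DLQI is mandatory, missing data are queried, and section 9.5 allows for patients who are not evaluable. The step 5 specificity figures also assume that every incomplete form crosses the cut, which step 2 rules out for one skip when the total is 5 or more. All of this stands, and it is why the point is minor. It does not remove the point, because no provision says when a form is unscorable.

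A second reply is that a limit on skipped items belongs in the SAP. That would hold if the protocol were silent, but it fixes both the scoring rule and the cut, so an SAP that follows it carries the error forward.

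A third is that leaving incomplete forms out does nothing for specificity. That is correct (step 7), and the fix has to include an analysis that can move it.

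A reader might also infer three stronger things that the document does not support:

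- **A contradiction over missing data.** "No replacement of missing data will be performed" stands under the secondary performance endpoints, and "The primary analysis will be performed with considering missing data as non responder" concerns goal achievement in section 9.8.4. Neither governs how a DLQI item is scored.
- **A bias in the tool's favour.** If skipping is unrelated to satisfaction, nearly all changes in the specificity verdict run from pass to fail.
- **That blank forms are meant to count as DLQI 0.** The literal wording allows it, but such forms may have been intended for the 10% not evaluable. The text does not settle this.

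**Conclusion.** The concern holds as a minor one. The stated scoring rule can place a patient with a true DLQI of 2 or more in the 0-1 column, and no other provision limits it. The error is one-directional in the reference standard; its direction in sensitivity and specificity depends on whether the moved patients are satisfied.

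Its size rests on an assumed 2-6% of incomplete forms. The upper bound is 0.5-1.6 of 27 forms and -1.3 to +0.1 points of sensitivity. With one randomly placed skip per form, at most 0.11-0.32 forms move. Several skips on one form, or skips that follow the patient's condition, could raise that second range. The 7.3% and 13.1% should not be read as expected probabilities. The study is exploratory, and reaching 85% leads only to further validation studies, so the issue counts only when a result lies near the threshold. The sample size of 134/150 is not affected.

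**What to change.** Amend sections 9.1.3 and 9.8.3 for the tables at 12/16 and 52 weeks, before the data are tabulated:

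- **(a)** An incomplete form whose answered items sum to 2 or more stays in the 2-or-more column.
- **(b)** A recorded 0-1 form with two or more unanswered items, including a blank form, is not evaluable and is left out. This cleans the sensitivity denominator; it cannot restore specificity.
- **(c)** Report two sensitivity analyses. One leaves out every recorded 0-1 form with any unanswered item, which tests sensitivity only. The other counts all those forms, except wholly blank ones, as 2 or more, which tests both measures. State whether the 85% verdict is the same in each.

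The second analysis in (c) is a bound, not an estimate, because it also moves incomplete forms from patients who are truly at 0-1. The one-item limit in (b) is a practical convention and does not follow from the DLQI classes. Add a sentence saying that this item-scoring rule is separate from the missing-data rules in sections 9.8.3 and 9.8.4.

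**Cost:** three short rules, two extra tables per time point and a check of the scoring program. Some forms become non-evaluable: at the assumed rates at most 134 x 0.02 = 2.7 to 134 x 0.06 = 8.0. The allowance is 150 - 134 = 16, which patients not evaluable for other reasons share.
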